3.3.3 Sampling Scheme

3.3.3.1 Sample Size

The student investigator calculated the sample size with the formula for two group comparison of means, exposed and unexposed groups for Cohort studies³⁶ by Epi-Info® -7 software. The outcome of the project is considered as a success if the difference between the intervening and comparison group in the first follow-up (O_1) assessment is 15% improvement in the patient-physician relationship percent score. From the existing literature of the other studies,³⁵ we assumed the baseline percent score of the patient-physician relationship to be 55.71% for both groups. After the intervention, the patient-physician relationship percent score is expected to increase to 64.07% in the intervention group in the first follow-up assessment (O_1).

The sample size is calculated based on the expected changes in the mean patient-physician relationship percent score in the intervention group of 15%. For variance, student investigator assumed that in both groups it will be equal. From a similar type of study,³⁵ the standard deviation of 2.5 was taken for calculation. Hence, the sample size was calculated to be one thousand one hundred and ninety eight (1198) in the intervention group and one thousand one hundred and ninety eight (1198) in the control group.

$$n_1 = n_2 = \frac{(Z\alpha/2 + Z\beta)^2 (\sigma_1^2 + \sigma_2^2)}{\Delta^2}$$

$$1198 = \frac{(1.96 + 1.28)^2 (2.5^2 + 2.5^2)}{(0.585)^2}$$

The literature shows that the response rate for similar types of evaluation studies have a response rate of 95%. Taking into consideration this information the estimated the sample size should be one thousand two hundred and sixty-two (1262) in each group.

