3.3.3.2 Sampling Scheme

For the selection of survey participants, the project team will use probability systematic random sampling. The survey will be conducted at the polyclinic as an exist survey, just after the patients' visit their family physicians. The survey will be conducted from Monday through Friday for 20 days. The survey hours will be from 09:00 to 13:00 in the respective months of the assessments in both polyclinics. The sample size for baseline and follow-up assessments each group in intervention and comparison is 1,262. To conduct the survey for 1,262 patients in twenty days, approximately sixty-four (64) surveys need to be conducted per day. The average numbers of patients visit the family physicians per weekday will be obtained (July 2015) from the administrators of the polyclinics. Then the interval between the survey participants will be calculated by dividing the number of visitors by nine for the baseline and follow-up assessments. After the patients' visit to the polyclinic, the supporting staff will approach to the patients. The patients, who have visited family physicians in the Heratsi and Muratsan polyclinics, will be asked to participate. The data will be collected through a self-administrated survey questionnaire. The supporting staff will collect the data from both polyclinics.

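### The printed sample-size formula gives 384 per group, not 1,198, and the figures of 1,262 per group and about 64 surveys per day inherit the error

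*Protocol*

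**What the plan says.** Protocol section 3.3.3.1 gives the general formula as "n_1 = n_2 = \frac{(Z\alpha/2 + Z\beta)^2 (\sigma_1^2 + \sigma_2^2)}{\Delta^2", with the two variances summed. The next line puts in the numbers and sets the result equal to the stated size: "1198 = \frac{(1.96 + 1.28)^2 (2.5^2 + 2.5^2)}{(0.585)^2". The inputs are also described in words: "the standard deviation of 2.5 was taken for calculation" and "For variance, student investigator assumed that in both groups it will be equal". Significance level and power appear only through 1.96 (two-sided 0.05) and 1.28 (90%).

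The text then concludes: "Hence, the sample size was calculated to be one thousand one hundred and ninety eight (1198) in the intervention group", and gives the same number for the control group. After allowing for a 95% response rate, "the estimated the sample size should be one thousand two hundred and sixty-two (1262) in each group".

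Section 3.3.3.2 carries this forward: "The sample size for baseline and follow-up assessments each group in intervention and comparison is 1,262". Spread over 20 survey days, it arrives at approximately 64 surveys per day. The Executive Summary repeats 1,262 per group.

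**The concern.** Both sides of the equation are the protocol's own, and they differ by a factor of about 3.1. No rounding convention or small-sample correction closes a gap of that size. The plan's main quantitative commitment therefore does not follow from the assumptions given for it, and the power implied by 1.28 is not the power that the stated size delivers.

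The practical stake is feasibility. Section 3.3.3.2 confines the survey to 09:00 to 13:00, so 64 per day means 64/4 = 16 completed forms an hour, against about 21/4 = 5 an hour on the printed formula. If each polyclinic must reach 1,262 within the 20 days, that rate applies at each site. Both follow-ups also exclude earlier respondents and patients registered after the baseline assessment, so the eligible pool is limited and a threefold overstatement draws on it without a stated reason.

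**Working it through.** **Inputs (all from section 3.3.3.1 unless noted).** z for alpha = 1.96; z for power = 1.28; SD = 2.5 in both groups; difference = 0.585; equal group sizes; response rate 95%; 20 survey days (section 3.3.3.2).

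**1. The printed formula.**
- (1.96 + 1.28)² = 3.24² = 10.4976
- 2.5² + 2.5² = 6.25 + 6.25 = 12.5
- 0.585² = 0.342225
- n = 10.4976 × 12.5 / 0.342225 = 383.4, so **384 per group**

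A standard two-means calculation (two-sided 0.05, 90% power) also gives 384.

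**2. Attempts to reproduce 1,198.** With difference 0.585 and SD 2.5, I varied sidedness, alpha (0.05 and 0.01) and power (80%, 90%, 95% and 99%). Results run from 226 (one-sided 0.05, 80% power) to 878 (two-sided 0.01, 99% power). None reaches 1,198. Multiplying the variances does:
- 6.25 × 6.25 = 39.0625
- 10.4976 × 39.0625 / 0.342225 = **1,198.2**

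**3. Dependent figures.**

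| Step | From 1,198 | From 384 |
|---|---|---|
| Divide by 0.95 | 1,261.05, so 1,262 | 404.2, so 405 |
| Divide by 20 days | 63.1, so 64 | 20.25, so 21 |

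These later steps are done correctly in the protocol and simply pass the error on.

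**4. Power on the stated inputs.** At 1,198 per group the standard error is 2.5 × √(2/1198) = 0.102, and 0.585/0.102 = 5.73. Then 5.73 − 1.96 = 3.77, giving about 99.99% power. At 384 per group, power is 90.0%.

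**5. Is 384 an adequate size?** That cannot be settled from the protocol.
- The same section expects a rise from 55.71% to 64.07%, which is 8.36 points and not 0.585. With 8.36 and SD 2.5 the formula gives 131.22/69.89 = 1.9, so 2 per group.
- One reading links the two: 3.9/7 = 55.71%, 4.485/7 = 64.07%, and 4.485 − 3.9 = 0.585 = 15% of 3.9. Delta and SD may therefore be on a 7-point scale. The protocol does not say so; this is an assumption.
- Section 3.3.1 also sets a 10% between-group difference at the second follow-up. If that means 10% of the assumed 3.9, the difference is 0.39 and n = 131.22/0.1521 = 862.7, so 863 per group. Power for 0.39 would then be about 58% at 384 and about 97% at 1,198. If it means 10 percentage points, fewer would be needed.

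**The case against.** The arithmetic cannot be defended: both printed lines show a plus sign, and although the section says that Epi-Info was used, it presents this equation as the calculation. The case on the other side is about how far the point reaches, and much of it stands.

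- **Cause.** A reader might conclude that the variances were multiplied. The match to the integer makes this a strong inference, but the protocol does not show the step. The finding does not need it.
- **Reach.** A reader might infer that every later count is wrong for this reason. That is not so. Section 3.3.3.2 derives the sampling interval by dividing visitors by nine, and Appendix 6 budgets 1018 completed questionnaires and 1080 for data entry. Nine × 20 days × 2 polyclinics × 3 assessments = 1,080. These counts do not come from 1,198 and are separate inconsistencies.
- **Waste.** It is tempting to compute a surplus of (1,262 − 405) × 6 = 5,142 questionnaires. The underlying total, 1,262 × 6 = 7,572, is never stated in the protocol and its budget does not fund it. Nor is 1,198 clearly excessive if the 10% objective is read as 0.39.
- **Rescue by another design.** One could note that a difference-in-differences contrast needs twice 383.4, so 767 per cell, and that 1,198/767 = 1.56 could be called a design effect. Section 3.3.3.1 defines success as a between-group difference at the first follow-up and sizes for that, so this would be a rationale supplied after the fact.
- **Stakes.** The error makes the sample larger. On the printed inputs it neither lowers power nor biases the estimate, and the burden on each respondent is a voluntary questionnaire of about 10 minutes.

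**Conclusion.** The finding holds in limited form. On its own inputs the printed formula gives 384 per group, so 1,198 is overstated about 3.1-fold (1198/384). The 1,262 per group (Executive Summary, sections 3.3.3.1 and 3.3.3.2) and about 64 surveys per day (section 3.3.3.2) inherit the error; their counterparts on the printed inputs are 405 and about 21. At 1,198 per group, power is about 99.99%, against the 90% implied. This rests only on the printed formula and inputs.

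The consequence is for feasibility and for the stated power, not for bias. A reader might go further and take 384 or 405 as the right size. The protocol does not support that, because the scale of 0.585 and 2.5 is not stated, 0.585 is not reconciled with the 8.36-point change, and the 10% objective may need about 863 per group under the assumption shown.

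**What to change.** 1. In section 3.3.3.1, correct the equation so that the printed expression equals 384 per group (405 after the 95% response rate), and restate the figures that depend on it in that section, in section 3.3.3.2 (including surveys per day) and in the Executive Summary.
2. Before fixing the final size, state the scale on which 0.585 and 2.5 are expressed. Reconcile both with the 55.71% to 64.07% change and with the 10% between-group objective in section 3.3.1, including whether that 10% is relative or in percentage points.
3. If a size near 1,198 is kept, report the power it gives on the stated inputs. Do not present it as the output of the printed formula, and do not attach a design-effect explanation to it afterwards.

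Steps 1 and 3 cost only wording and number changes and need no extra patients. Step 2 means going back to the source of the SD and the difference; the final size could lie above 384, and its cost cannot be given until that is done.

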3.3.3.2 Sampling Scheme

For the selection of survey participants, the project team will use probability systematic random sampling. The survey will be conducted at the polyclinic as an exist survey, just after the patients' visit their family physicians. The survey will be conducted from Monday through Friday for 20 days. The survey hours will be from 09:00 to 13:00 in the respective months of the assessments in both polyclinics. The sample size for baseline and follow-up assessments each group in intervention and comparison is 1,262. To conduct the survey for 1,262 patients in twenty days, approximately sixty-four (64) surveys need to be conducted per day. The average numbers of patients visit the family physicians per weekday will be obtained (July 2015) from the administrators of the polyclinics. Then the interval between the survey participants will be calculated by dividing the number of visitors by nine for the baseline and follow-up assessments. After the patients' visit to the polyclinic, the supporting staff will approach to the patients. The patients, who have visited family physicians in the Heratsi and Muratsan polyclinics, will be asked to participate. The data will be collected through a self-administrated survey questionnaire. The supporting staff will collect the data from both polyclinics.

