3.2 Implementation Plan Synopsis

3.2.1 Program

We proposed to implement the Physician Leadership Development Program to the family physicians of Heratsi polyclinic, which is under the administration of Yerevan State Medical University. During the program, the core training personnel will consist of two physicians who have taken “training of trainers” course. These physician trainers should have a Master of Public Health (MPH) degree from the American University of Armenia. The trainers will take the free online course “Edward Jenner Program” provided by Leadership Academy in National Health Services, United Kingdom.³⁴ The trainers will complete the course and obtain a certificate. On completion of the online program, the trainers will use these materials to teach the family physicians. The trainers will also translate the online program materials into Armenian. The training course includes topics not only about the leadership (as a core component), but also about cooperation, planning, resource management, innovation in patient care, assessment of outcomes of patient care and decision-making.

The program consists of 21 sessions (each 40 minutes), three sessions a week in a seven-week period. The physicians in the primary health centers work on two shifts; Morning shift: (9:00 AM -1:00 PM) and afternoon shift (1:00 PM - 5:00 PM) for six days a week. Each physician has his/her schedule on even and odd days of the week. Separate sessions will be offered to two cohorts on even and odd days of the week. The session will conduct on each day of the week from 2:00 PM until 3:30 PM with a break of fifteen minutes. No session will schedule for Sundays. The sessions will be conducted at the American University of Armenia.

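### The sampling interval is built from whole-weekday visitor counts but applied only from 09:00 to 13:00, so the rule misses its own daily target and no afternoon visit can be selected

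*Protocol*

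**What the plan says.** All references are to the Protocol.

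- **Survey window (3.3.3.2 Sampling Scheme).** "The survey hours will be from 09:00 to 13:00 in the respective months of the assessments in both polyclinics". Also: "The survey will be conducted from Monday through Friday for 20 days".
- **Daily target (same section).** For 1,262 patients per group at each assessment, "approximately sixty-four (64) surveys need to be conducted per day".
- **Interval (same section).** "The average numbers of patients visit the family physicians per weekday will be obtained" in July 2015 from the polyclinic administrators. The interval is then that number of visitors divided by nine, at baseline and at follow-up. The scheme is described as systematic random probability sampling.
- **Clinic hours (3.2.1 Program).** Physicians work in two shifts: "Morning shift: (9:00 AM -1:00 PM) and afternoon shift (1:00 PM - 5:00 PM) for six days a week". Further: "Each physician has his/her schedule on even and odd days of the week".
- **Target population (3.3.2 Study Settings and Target Population).** Family physicians' patients who are registered and treated at the polyclinic, with no limit by time of day.

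No section restricts the July count to the morning, and no afternoon or Saturday survey is planned.

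**The concern.** A systematic sample reaches its planned size only if the visitor count behind the interval covers the same period in which the interval is applied. Here the count is per weekday and the survey covers one of two four-hour shifts. Field staff who follow the rule will fall short every day, and the likely response is an improvised change to the interval, which would make the selection probabilities unknown.

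The second issue is coverage. A visit after 13:00 has no chance of selection. A patient who attends only in the afternoon during the 20 days is therefore left out, although the target population includes that patient. The threats to validity listed under Evaluation Study Design do not mention time of day.

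**Working it through.** **Inputs from the Protocol.** Sample size 1,262 per group per assessment, 20 survey days, daily target 64, divisor nine (all 3.3.3.2); 1,198 before allowance for non-response and a 95% response rate (3.3.3.1).

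**Input not in the Protocol.** The share *s* of weekday visits that fall between 09:00 and 13:00. The shifts are equal in hours, but visits by shift are not given. I assume 50% and show 30% to 70%.

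**Step 1: the plan's own figures.** 1,198 / 0.95 = 1,261.05, rounded up to 1,262. 1,262 / 20 = 63.1, rounded up to 64. Both reproduce.

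**Step 2: yield of the rule.** Let *V* be visitors per weekday and *d* the divisor. The interval is *k* = *V*/*d*. Visitors in the survey window number *sV*. Selected per day = *sV*/*k* = *s* × *d*. *V* cancels, so the unknown visitor count does not affect the result.

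**Step 3: numbers.**

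| Divisor | Share *s* | Per day | In 20 days | Shortfall against 64 |
|---|---|---|---|---|
| 9 (as written) | 0.3 | 2.7 | 54 | 96% |
| 9 | 0.5 | 4.5 | 90 | 93% |
| 9 | 0.7 | 6.3 | 126 | 90% |
| 9 | 1.0 (count matches window) | 9 | 180 | 86% |
| 64 | 0.3 | 19.2 | 384 | 70% |
| 64 | 0.5 | 32 | 640 | 50% |
| 64 | 0.6 | 38.4 | 768 | 40% |
| 64 | 0.7 | 44.8 | 896 | 30% |
| 64 | 1.0 (count matches window) | 64 | 1,280 | none |

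**Step 4: separating the two errors.** The divisor alone takes 64 per day down to 9, a factor of about 7. The hours mismatch alone, at an even split, halves whatever the divisor gives (64 to 32, or 9 to 4.5). Correcting either one without the other still misses the target.

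**Step 5: completed questionnaires.** The table counts patients approached. With 95% response and divisor 64, 640 / 768 / 896 approached give about 608 / 730 / 851 completed, against 1,198. With both corrections, 1,280 × 0.95 = 1,216, which meets 1,198.

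**Origin of the nine (inference only).** 9 per day × 20 days × 2 polyclinics × 3 assessments = 1,080, the number of questionnaires in the data-entry footnote of Appendix 6. Nine may be the daily target of a smaller design.

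**The case against.** **The yield problem belongs to the divisor.** Largely true. Under the written rule the shortfall is about 93% at an even split, and nine would give only 9 per day even if the count matched the window. A reader might infer that the survey hours make the target fall short by about half. The Protocol does not support that figure: it needs a divisor of 64, which is not the stated one, and an even split of visits, which is not given. What stands is that the mismatch of hours remains after the divisor is corrected.

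**The weekday count could be meant as a morning count.** Possible, but no wording says so. If it were, only the divisor error would remain.

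**Afternoon patients are not wholly excluded.** Also fair. A reader might infer that they have zero chance of selection. Zero chance attaches to afternoon visits: a patient may be selected at a morning visit, and since physicians' schedules differ between even and odd days, no physician's patients are shown to be left out altogether. The exclusion is certain only for patients who attend solely after 13:00 (or on Saturday) in the survey period. Nor does the Protocol support a claim about people who attend after work, since both shifts end by 17:00.

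**The comparison is not biased.** A reader might infer bias between polyclinics. The same window applies in both and at all assessments, so none is shown. Systematic sampling within a stated morning frame is legitimate; the fault is that the frame is not stated and does not match the target population.

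**The sample size is itself unsound.** With the printed inputs of section 3.3.3.1, (1.96 + 1.28)² × 12.5 / 0.585² = 383.4, so 384 per group rather than 1,198. On that figure 608 completed would suffice, and loss of power from the hours mismatch alone is not established. The written rule would still fall short: 90 × 0.95 is about 86. In either case the rule does not deliver the 64 per day that the same section requires.

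**Conclusion.** The point holds. The interval uses a count for the whole weekday and is applied to the morning only, so the number selected per day is the morning share times the divisor. As written, that is about 4.5 per day and 90 in 20 days, instead of 64 and 1,262, at an assumed 50% morning share (54 to 126 in 20 days for shares of 30% to 70%). With the divisor corrected to 64 and nothing else changed, it is about 32, 38 or 45 per day for assumed shares of 50%, 60% or 70%. The shares are assumptions; the formula and the direction of the error are not.

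Visits after 13:00 cannot be selected, which does not fit the stated target population. The consequences are for attained sample size and representativeness, not, on the evidence of the Protocol, for the validity of the contrast between polyclinics. The correction is cheap and belongs in the plan before fieldwork.

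**What to change.** In section 3.3.3.2:

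1. Compute the interval as the July 2015 average number of visitors **in the surveyed window**, divided by **64** instead of nine. This gives 64 per day and 64 × 20 = 1,280 in 20 days, provided that each window has at least 64 eligible visitors. The July counts will show whether it does.
2. Alternate the four-hour window by week: 09:00 to 13:00 in weeks 1 and 3, 13:00 to 17:00 in weeks 2 and 4, with the same calendar in both polyclinics and at all three assessments. Alternation by week is preferable to alternation by even and odd day, because physicians' schedules follow even and odd days and each Monday-to-Friday week contains both.
3. If the afternoon survey is not feasible, keep the morning window with the interval from item 1, and state that the sampled population is weekday-morning attenders.
4. State in either case that Saturday visits are outside the frame.

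**Cost.** Revised field-schedule wording and the same staff hours. The July counts must be requested by shift. If the two shifts differ in volume, selection probabilities per visit differ between them (64 over the window's visitor count), but they are known and can be used as weights.

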Appendix 6: Budget in Armenian Drams (AMD)

Budget Item	Type of appointment	Type of Appointment	Number of Units	Amount/Unit	Total
Personnel Fee					
Project Coordinator	Full Time	Fixed Monthly	14	150,000.00	2,100,000.00
Training Personnel (For taking the online Edward Jenner Program and translating the materials)	Fixed Hours (Flexible)	One Time	2	150,000.00	300,000.00
Training Personnel (For preparing and conducting the sessions)	Fixed Hours	Hourly	63*	10,000.00	630,000.00
Supporting Staff (For conducting the survey)	Flexible	Each Completed Questionnaire	1018	150.00	152,700.00
Supporting Staff (Transport compensation for conducting the survey)	Flexible	Day	90	400.00	3,600.00
Supporting Staff (Data Entry and Cleaning)	Part-Time	Hour	90†	1,500.00	135,000.00
Sub Total					3,321,300.00

* 63 Hours = (21 session) * (each session 1.5 hr.) * (two cohort)

† 90 Hours = (1080 questionnaires) * (5 Minutes/questionnaire)

Budget Item	Type of appointment	Type of Appointment	Number of Units	Amount/Unit	Total
Overhead Costs					
Administrative Costs					
Class Room Rentⁱ	Flexible Fixed Hours	Hourly	63	10,000.00	630,000.00
Office Room Rent	Full Time	Monthly	14	120,000.00	1,680,000.00
Paper Cost & Print	N.A	Per Piece	5000	10.00	50,000.00
Office Supplies	N.A.	N.A.	N.A.	100,000.00	100,000.00
Communication Costs					
Phone Land Line & Internet	Full Time	Monthly	14	15,000.00	210,000.00
Mobile Phone	Part Time	Monthly	3	5,500.00	16,500.00
Sub Total					2,686,500.00
Grand Total[#]					6,007,800.00

#Grand Total includes Income Tax and VAT

ⁱ 18 Person Seminar Room

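### The sampling interval (weekday visitors divided by nine) selects nine patients a day, but the same section requires about 64 a day to reach 1,262 per group per assessment

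*Protocol*

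**What the plan says.** Section 3.3.3.2 (Sampling Scheme) fixes the number, the duration and the daily load:

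- "The sample size for baseline and follow-up assessments each group in intervention and comparison is 1,262"
- "The survey will be conducted from Monday through Friday for 20 days"
- "approximately sixty-four (64) surveys need to be conducted per day"
- "The survey hours will be from 09:00 to 13:00 in the respective months of the assessments in both polyclinics"

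The same paragraph then sets the selection rule. The visitor count comes from the clinics: "The average numbers of patients visit the family physicians per weekday will be obtained (July 2015) from the administrators of the polyclinics". The sampling interval is then "calculated by dividing the number of visitors by nine for the baseline and follow-up assessments". No other meaning is given for nine, and there is no rule for topping up a day that falls short of 64.

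Appendix 6 costs data entry on a different scale: "90 Hours = (1080 questionnaires) * (5 Minutes/questionnaire". Its line for paying survey staff per completed questionnaire lists 1,018 units.

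**The concern.** In systematic sampling the interval determines how many patients are approached. A divisor of nine and a quota of 64 a day differ about sevenfold, and both stand as instructions in one paragraph. If staff apply the interval, the survey stops far short of the stated sample. If they apply the quota, they must invent an interval. They might do so differently by polyclinic or by assessment, which would weaken the claim to probability sampling and the comparability of the three surveys. The data-entry budget agrees with nine and not with 64, so the mismatch is not confined to one digit.

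**Working it through.** **Inputs.** From 3.3.3.2: target 1,262 per group per assessment, 20 days, divisor 9, survey window of 4 hours. From 3.3.3.1: z-values 1.96 and 1.28 (90% power), SD 2.5 in both groups, difference 0.585, completed sample 1,198, response rate 95%. From 3.3.2 (Evaluation Study Design): 2 groups and 3 assessments. From Appendix 6: 1,080 questionnaires at 5 minutes each, 1,018 payment units, 150 AMD per questionnaire, 1,500 AMD per data-entry hour. The weekday visitor count V is not given and is not needed.

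**The plan's own daily figure.** 1,198 / 0.95 = 1,261.05, rounded up to 1,262. 1,262 / 20 = 63.1, rounded up to 64. Both reproduce.

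**Yield of the interval rule.** With k = V/9, the number selected per day is V/k = 9, and V cancels.

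- Approached: 9 × 20 = 180 per group per assessment. Rounding k down gives 180 to 188 for the values of V tried, from 64 to 576.
- Responding: 180 × 0.95 = 171.
- Share of target: 180 / 1,262 = 14.3%.
- Days needed for 1,262 at nine a day: 1,262 / 9 = about 140.

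This assumes that V counts the patients seen while the survey runs. Section 3.2.1 describes a morning and an afternoon shift, and the survey covers only the morning. If V covers the whole day and a share s of visits falls between 09:00 and 13:00 (assumed; not in the protocol), the yield is 180 × s: 180 for s = 1, 135 for s = 0.75, 90 for s = 0.5.

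**Yield with 64.** 64 × 20 = 1,280 approached and 1,280 × 0.95 = 1,216 responding, which covers 1,262 and 1,198.

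**Other readings of nine.**

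- Nine per survey hour: 9 × 4 × 20 = 720, still short; 64 a day is 16 an hour.
- Nine as the interval itself (every ninth patient): 64 a day would need 64 × 9 = 576 visitors. The protocol gives no such count, and the sentence says to divide by nine.

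**Power if the interval rule is followed.** Power ≈ Φ(Δ / (SD × √(2/n)) − 1.96).

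- Δ = 0.585, n = 180: 0.585 / (2.5 × √(2/180)) = 2.22; power about 60%.
- Δ = 0.585, n = 171: 0.585 / (2.5 × √(2/171)) = 2.16; power about 58%.
- Δ = 64.07 − 55.71 = 8.36, with SD 2.5 on the same scale: power near 100% at either n.

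**Is the target itself sound?** The printed formula gives (1.96 + 1.28)² × 12.5 / 0.585² = 383.4, that is 384 and not 1,198. Inflated for response, 384 / 0.95 = 404.2, or 405. 405 / 20 = 20.25, so 21 a day. The interval's yield of 180 is below this target too.

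**Budget cross-check.**

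- 1,080 / (2 × 3) = 180, exactly the yield of nine a day. 1,018 / 6 = 169.7.
- 1,262 × 6 = 7,572 questionnaires. Payment: 7,572 × 150 = 1,135,800 against 152,700, a rise of 983,100 AMD. Data entry: 7,572 × 5 / 60 = 631 hours × 1,500 = 946,500 against 135,000, a rise of 811,500 AMD. Together 1,794,600 AMD, about 30% of the 6,007,800 total.
- Counting only completed questionnaires, 1,198 × 6 = 7,188: 925,500 + 763,500 = 1,689,000 AMD.
- 405 × 6 = 2,430 questionnaires: (364,500 − 152,700) + (303,750 − 135,000) = 380,550 AMD.

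**The case against.** The contradiction itself has no good answer, but four limits on it do stand.

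- *Staff are also told that 64 a day are needed.* A reader might infer that the study will collect only 14% of its sample. That follows only if the interval overrides the quota in the same paragraph, and the shortfall would show on the first survey day. The protocol does not say which instruction prevails.
- *The loss of power depends on the effect taken.* Against 0.585, the value in the formula, it is large. Against the 8.36 points in the prose of 3.3.3.1 there is practically none, provided the SD of 2.5 is in percent points. The protocol does not state the scale of 0.585 or of the SD.
- *Nine looks like a remnant of a smaller plan.* The match between 1,080 and 180 × 6 invites that inference, but the protocol nowhere says so. The same budget also lists 1,018 questionnaires, so it is not consistent on this itself. The target could equally be the figure that was changed without carrying the change through.
- *Comparing changes from baseline between polyclinics would be weaker still.* A reader might want to add the power of a difference-in-differences test. Section 3.3.1 sets its between-group objective at follow-up, section 3.3.3.1 defines success by the group difference at the first follow-up, and section 3.3.5 names t-tests and linear regression. No such test is planned, so its power is no measure of this error.

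**Conclusion.** The point holds as an internal contradiction in section 3.3.3.2. Nine a day and 64 a day cannot both be carried out. The interval rule gives about 180 approached and 171 responding per group per assessment, against 1,262 and 1,198. This does not depend on the visitor count, and 180 is the upper end if that count covers the whole clinic day. If the rule is followed, power is 58–60% instead of 90% on the printed difference of 0.585 and SD of 2.5. That statement rests on those two inputs and does not carry over to the 8.36-point change. The protocol supports a demand to reconcile target, interval and budget. It does not establish which of them is wrong.

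**What to change.** Settle the target per group per assessment first, then make the rule match it.

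- *If the target stays above 180:* define the interval as the expected number of family-physician visitors between 09:00 and 13:00, divided by the required surveys per day. The divisor is 64 for 1,262, or 21 for 405, the printed formula's actual result inflated for 95% response. Ask the polyclinics for the count in that window, not for the whole weekday.
- *If nine is kept:* restate the sample size as 180 approached (171 responding) per group per assessment, with the power that this gives, and remove the 64-a-day quota. The visitor count must again refer to the survey window.

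The wording change is short, but the cost is not one number, because Appendix 6 has to follow. Keeping 1,262 means 7,572 questionnaires and about 1.8 million AMD more (about 1.7 million if only completed ones are counted); the 5,000 printed pieces budgeted would not cover one sheet each. A target of 405 means 2,430 questionnaires and about 0.38 million AMD more. Keeping 180 leaves the data-entry line as it is, but the 1,018 payment units and the 1,080 entry units still need to be reconciled.
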